### **Inclusion Criteria:**

- Age  $\geq$ 18 years
- Primary speaking language is English or Spanish.
- Patient is on chronic in-center HD prior to randomization
- HD takes place at one of the participating Dialysis Clinic Inc. (DCI) sites during the data collection period.
- Subject urinates more than 200 ml of urine a day (self-reported).
- Patients must be willing and able to sign the consent form.

### **Exclusion Criteria:**

- Age  $<$ 18 years of age.
- RRF  $<$ 2 mL/min/1.73 m^2 as determined by 24-hour urine collection.
- Allergy or contraindication to bumetanide.
- Expectation that native kidneys will recover.
- History of poor adherence to treatment.
- Unable to verbally communicate.
- Requires more than 3 HD treatments per week due to medical co-morbidity (such as, but not limited to: severe volume overload requiring frequent HD e.g. in systemic oxalosis, or requiring total parenteral nutrition).
- Scheduled for living donor kidney transplant in the next 6 months.
- Intention to change to peritoneal dialysis, or home HD in the next 6 months.
- Plan to relocate to another center within the next 7-8 months.
- Expected geographic unavailability at a participating HD unit for  $>$ 2 consecutive weeks or  $>$ 4 weeks total during the next 6 months (excluding unavailability due to hospitalizations)
- Post kidney transplantation

# DIDIT: Diuretic/Cool Dialysate Trial

- Currently in an acute or chronic care hospital
- Life expectancy <6 months or intention to withdraw dialysis therapy within 6 months.
- Current pregnancy, nursing mother or actively planning to become pregnant in the next 8 months
- Current use of investigational drugs
- Participation in another non-observational clinical trial that contradicts or interferes with the therapies or measured outcomes in this trial
- Unable or unwilling to follow the study protocol for any reason (including mental incompetence)
- Unable or unwilling to provide informed consent or sign IRB-approved consent form.

The following special populations will not be included in this study:

- Patients who are too infirm or lack the capacity to meaningfully participate in medical decisions and to sign the informed consent form.
- Children and adolescents constitute <2% of the dialysis population, and our preliminary survey of the study sites found no children and adolescents were active patients. In any case, the renal and other physical factors of children and adolescents with ESRD are not directly comparable to those of adults.
- Prisoners.

The study is open to all volunteers, regardless of gender, race, ethnicity, or sexual preference. All study consents and documents will be in English or Spanish, except for the PROMIS-57, which is currently unavailable in Spanish. Patients who are Spanish speaking only will not complete this questionnaire. If the questionnaire becomes available, we will add it with IRB approval.

## 5. Number of Subjects

Up to 50 patients may be recruited/consented for this study.

It is unknown, at this time, how many eligible subjects will need to be approached in order to attain the desired number of study participants. We will continue to recruit until 20 patients have been followed to completion post protocol modification.

## 6. Study Timelines

- The duration of an individual subject's participation in this research is 8 months.
- Subject recruitment will occur over 18 months.
- See table 1 "*Schedule of study tests/assessments/intervention*", Study Procedures section 12, for procedure timeline.
- Anticipated data collection is to be completed by the end of year 2. Once all data has been collected and verified, data analysis and report preparation will take place over a 6 month period.

## 7. Study Endpoints

# DIDIT: Diuretic/Cool Dialysate Trial

- Recruit and randomize 25 incident chronic in-center HD patients with urine output >200 mL/day and to 3 mg of oral bumetanide once daily and/or to cool dialysate (35.5 °C).
- Estimate recruitment and retention rates anticipated in a full-scale study.
- Compare changes in RRF markers between groups.
- Collect preliminary data on adverse events (AE) and serious adverse events (SAE), biomarkers of inflammation and injury to native kidneys, HRQOL, health care utilization and other potential outcomes of a full-scale trial.

## 8. Research Setting

Potential subjects will be recruited at Dialysis Clinic Inc. (DCI) centers located in Albuquerque and Rio Rancho.

Pre-dialysis and 24 hour urine collections will take place at the participant's home. As appropriate to the study timeline, lab values will be collected from the participant's DCI records.

Study blood samples collected at DCI will have their initial spin done at DCI by study personnel using DCI's centrifuge. These samples and any collected urine samples will be transported to a UNM study lab or to a Tricore® lab for final processing. No collected specimens will be sent to DCI laboratory.

## 9. Resources Available

[name], MD is the UNM Nephrologist overseeing this study. This site has been granted approval to recruit and complete study visits at the Albuquerque, New Mexico Dialysis Clinics Inc. and the Rio Rancho clinic. The PI, sub-investigators, biostatistician, micro-RNA specialist, lab staff and study coordinators and research assistants make up the study team. This team has broad expertise to successfully complete the proposed aim and efficiently deliver findings for immediate clinical and public health application.

Study physicians will be responsible for medical decision-making, and for ordering and the evaluation of necessary diagnostics and therapeutics for this study.

The 20 recruited/consented subjects that will complete this study will be recruited at the four DCI clinics in Albuquerque and at the Rio Rancho DCI clinic. The four DCI study sites should be able to supply the research subjects needed to be recruited for this study.

Recruitment will last 18 months. An additional 6 month period will be used to complete the intervention in the last subjects.

The study investigators recognize that recruitment is the major factor for a successful RCT and will use a multi-faceted approach to enhance recruitment. First, the

# DIDIT: Diuretic/Cool Dialysate Trial

nephrologists and staff of the dialysis units will be informed of the study and will provide materials to help explain the importance of study participation. The physicians and dialysis staff will also be educated on the study rationale and the scientific importance of study participation. The dialysis clinics and nurse educators will be provided with brochures and posters that will be conspicuously displayed in the dialysis clinic waiting areas. Special attention will be placed on the recruitment of minority participants.

## 10. Prior Approvals

The following approvals have been obtained for this study:

- Bumetanide drug form attachment
- Departmental Scientific Review Form

## 11. Multi-Site Research

This is not a multi-site study

## 12. Study Procedures

**Table 1: Schedule of the study tests/assessments/intervention during the pre-trial (4 wks), intervention (24 wks or 6 months) and post-trial periods (4 wks).**

		Study Phases →	p r e	intervention						p o s t	Time to do
	Measurements/Tests	Month →	0	1	2	3	4	5	6	7	
Intervention	Randomization Intervention: (to one of the following arms) 

• Cool dialysate and placebo

• Cool Dialysate and Bumetanide (3mg/day)

• Isothermic dialysate and placebo

• Isothermic dialysate and Bumetanide (3mg/day)

		X								
	Issue (Bumetanide or placebo): For participants whose pre-intervention 24-hour urinary Creatinine and Urea clearance results allow them to complete the study, any current diuretic will be discontinued prior to taking the "study drug".			X			X				During Dialysis
	Bumetanide/placebo compliance check						X		X		
Blood tests & HD Rx	Routine: (Obtain from DCI monthly labs) 

• Albumin (g/dL)

• Hemoglobin (g/L)

• Intact parathyroid hormone (pg/ml)

• Kt/V

• Potassium (mEq/L)

• Calcium (mg/dL)

• Sodium (mEq/L)

• BUN (mg/dL)

• Creatinine (mg/dL)

		X	X	X	X	X	X	X	X	Collect with DCI monthly labs if values are older than 30 days
	Additional blood tests: [Total blood: 11ml: 10ml collected; 1ml waste] 

• B2-microglobulin (drawn pre- and post-HD)

• Cystatin

• NGAL

• KIM-1

• CRP (mg/L)

		X		X			X			Collected with DCI monthly labs

# DIDIT: Diuretic/Cool Dialysate Trial

Questionnaire	
 
IL-6
 
TNF-<math>\alpha</math>
 
IL-1<math>\beta</math>
 
								
	microRNA (drawn pre- and post-HD) [Total blood: 8mls; no waste]	X				X			
	Pregnancy testing (blood serum testing) [1ml]	X							Prior to randomization
	HD treatment data collected: (From DCI pt. Chairside flow sheet)	X	X	X	X	X	X	X	
	
 
HD Run time
 
Membrane type
 
Dialysate bath
 
QB (Blood flow rate: BFR ml/min)
 
QD (Dialysis fluid flow rate: DFR ml/min)
 
UF (Ultrafiltration) time
 
BP (Every 30 minutes and min & max)
 
Pre & Post dialysis weight
 
Height (one time only)
 
								
	•								
	
 
Dialysis Symptom Index
 
PROMIS-57
 
	X		X		X			
									phone or in person (30 minutes)
	Charlson comorbidity index (CCI) and underlying kidney disease	X		X		X	X	3-5 min	Study Staff
	Medications: 
 
In-center 
 
EPO
 
Iron
 
Vitamin D
 
 
 
Outpatient medications
 
	X	X	X	X	X	X	X	
Comorbidity & Clinical data	Demographics: 
 
Age
 
Gender
 
Race
 
Ethnicity
 
Marital status
 
	X							
	Adverse Events: 
 
Emergency room visits
 
Hospitalization(s)
 
Outpatient visits
 
Mortality
 
Transplantation
 
PD (Peritoneal dialysis)
 
Transfer to other unit
 
Relocation
 
Hypotensive episode
 
Dialysis access event 
 
Clotting
 
Stenosis
 
Revision
 
New graft or catheter
 
 
 
	X	X	X	X	X	X	X	
	History and physical exam by MD (PI, sub-I or their designees)	X							
	24 hour urine collection: RRF 
 
Start collecting urine day before midweek dialysis session (Note date/time)
 
Stop collecting urine 24 hours later (Note date/time) 
 
Creatinine
 
Urea
 
o
 
 
 
	X		X		X			Collected before a midweek dialysis session
	*Urine fresh void: [20mls] 
 
Urinary cystatin C
 
Urine creatinine
 
uNGAL
 
	X		X		X			Collected before dialysis session

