# DIDIT: Diuretic/Cool Dialysate Trial

## 1. Objectives

Each year in the United States, approximately 100,000 people start maintenance dialysis therapy suffering high mortality rates, frequent hospitalizations, and marked decline in quality of life. The overarching aim of the “**Diuretic/Cool Dialysate Trial**” (DIDIT) is to improve outcomes of incident hemodialysis (HD) patients by recognizing the importance of residual renal function (RRF). This pilot study will demonstrate the feasibility of loop diuretic (bumetanide) use and/or cool dialysate, and will obtain preliminary information that will inform future examination into whether these interventions will slow the rate of RRF decline in HD, improve quality of life, and reduce overall mortality.

The proposed pilot study challenges the current widespread paradigm of discontinuing loop diuretics when initiating chronic HD and/or maintaining the dialysate at a constant temperature of 37 °C for all patients.

**Specific Aim:** We aim to conduct a pilot randomized controlled trial (RCT) to assess feasibility and safety, and to inform the design of a full-scale trial of bumetanide and/or cool dialysate using a two-by-two factorial design, compared to usual care.

The long-term goals of this proposed work are to optimize survival, health-related quality of life (HRQOL) and other outcomes of HD patients by providing them a low dose of a loop diuretic and by lowering the dialysate temperature at the start of their transition to dialysis therapy. The design will permit a rapid scaling-up of the interventions to a larger clinical trial since the incremental dialysis prescription takes advantage of resources and personnel that are readily available. This pilot study will substantially accelerate our ability to address fundamental issues in the care of this population, which is burdened by low HRQOL and can change the current paradigm and practice pattern.

**Hypothesis:** Use of bumetanide and/or cool dialysate during the first six months of HD will slow the rate of RRF decline, decrease inflammation and oxidative stress, improve HRQOL and decrease mortality. To explore this hypothesis we propose to conduct a pilot RCT.

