## DIDIT: Diuretic/Cool Dialysate Trial

Diuretic therapy remains the cornerstone of managing fluid overload. The role of diuretics in managing HD patients is not yet clearly defined (1). Diuretics can be used to minimize RRF loss in chronic HD patients (1). More specific loop diuretics are not nephrotoxic, confer better fluid balance, maximize urine production, allow less aggressive ultrafiltration and are associated with decreased cardiac mortality (1, 2). The DOPPS study verified that loop diuretics are the most often prescribed diuretics to chronic HD patients (2). In clinical practice, many patients begin HD chronically using small doses of a loop diuretic, but since there is little evidence that these are beneficial, their use is suspended when the volume of residual diuresis is reduced to minimum values.

While currently not the standard of care in the US, cool dialysate may confer significant survival benefits. Cool dialysate has been associated with decreased intradialytic hypotension which may minimize kidney injury and slow RRF decline. The current US paradigm is to maintain dialysate temperature according to physician's discretion, usually at 37 °C. Cool dialysate may decrease inflammatory and oxidative stress from HD therapy, and thus minimize kidney injury, slow the decline of RRF, and decrease morbidity and mortality. This important strategy of preserving RRF is not routinely applied to HD patients.

The use of bumetanide is also not currently the standard of care, but additionally may provide survival benefits by minimizing RRF loss. Specifically, bumetanide is not nephrotoxic, confers better fluid balance, maximizes urine production, may allow less aggressive ultrafiltration and is associated with decreased cardiac mortality.

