### **3. Study Design**

This pilot RCT will demonstrate the feasibility and safety of performing a large scale study of diuretic use and/or cool dialysate by examining recruitment, retention, and key outcomes. This study will further assess whether the use of a diuretic compared to non-use of a diuretic (placebo) and/or the use of cool dialysate (35.5 °C) compared to 37 °C for up to 6 months will improve RRF, improve HRQOL and reduce hospitalizations. by randomizing 20 chronic hemodialysis patients from DCI centers in the greater Albuquerque area, to either bumetanide and cool dialysate randomized in a two-by-two factorial distribution.

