# DIDIT: Diuretic/Cool Dialysate Trial

No Diuretic (placebo) and 37°C dialysate	No Diuretic (placebo) and 35.5°C dialysate
Diuretic and 37°C dialysate	Diuretic and 35.5°C dialysate

The study sample will be selected using an approach to limit drop-out while enhancing generalizability and the main analysis will be intention-to-treat. *Considering the intervention cannot be double-blinded, we have made efforts to reduce bias by using objective outcomes and blinding the assessment of patient-reported outcomes.* Subjects will be recruited for 18 months. An additional 6 month period will be used to complete the intervention in the last subjects and they will be re-assessed at month 8 for an end of study evaluation. The recruitment and participation parameters for development of this formal RCT will assess whether the large scale study can meet enrollment criteria and target timelines, and whether patients can be maintained on the study protocol without safety concerns.

In this pilot study we will assess as primary patient outcomes:

- The change in RRF over 6 months
- The association of cool dialysis and/or diuretic with inflammation
- The association of cool dialysis and/or diuretic use with acute kidney injury (AKI) biomarkers.

The secondary patient outcomes will be:

- Change in HRQOL
- Time to first-hospitalization.

Being a pilot study, our focus is on assessing whether changes in RRF can be detected with the proposed technique (urinary creatinine and urea clearance). Biomarkers of inflammation and AKI will be collected to supplement the functional measurement of renal filtration and as surrogate biomarkers of benefit or safety (e.g. nephrotoxicity) that can be monitored in the large scale study.

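### Table 1 lists no dialysate temperature and checks compliance only for the study drug, so the planned data cannot document whether the assigned temperature was delivered

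*Combined protocol and SAP*

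**What the plan says.** Section 3 randomizes patients in a two-by-two design in which one factor is "the use of cool dialysate (35.5 °C) compared to 37 °C for up to 6 months".

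Section 1 sets the purpose: "This pilot study will demonstrate the feasibility of loop diuretic (bumetanide) use and/or cool dialysate". Section 3 adds that the pilot is to learn "whether patients can be maintained on the study protocol without safety concerns".

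Section 12, Table 1, has a row headed "HD treatment data collected: (From DCI pt. Chairside flow sheet"). Its items are run time, membrane type, dialysate bath, blood flow, dialysate flow, ultrafiltration time, blood pressure, weight before and after dialysis, and height. Neither a set nor a measured dialysate temperature is among them.

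The one compliance row in Table 1 is "Bumetanide/placebo compliance check". Section 33 has the coordinator track compliance with the study drug each month. No section has a counterpart for the dialysate. Section 18 provides for monitoring of comfort and cold intolerance, which concerns tolerability.

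The control temperature is given as 37 °C in Section 3, while the arms in Table 1 use labels such as "Isothermic dialysate and placebo" with no figure.

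**The concern.** A pilot that tests two interventions should be able to say, for each, how often patients received what they were assigned. This plan can do so for the pill. For the dialysate, a patient could stay in the study for six months, complete every assessment and count as retained, with nothing in the listed data to show the temperature of any session.

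At stake is the feasibility answer itself. The full-scale trial would start without an estimate of how often the assigned temperature was run, in either the cool or the control arms, and without the average difference in set temperature between them. These are design inputs that a pilot is well placed to supply.

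**Working it through.** The plan gives no figure for delivery of either intervention, so there is none to reproduce. Its one precision statement, ±0.18 with 20 patients in Section 13, concerns retention. It follows from 1.96 × √(p(1 − p)/20) if p is about 0.79: 1.96 × √(0.79 × 0.21/20) = 0.179. It says nothing about temperature.

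**Step 1. Provisions for the two factors, side by side.**

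| Provision | Bumetanide/placebo | Dialysate temperature |
|---|---|---|
| Assigned level stated | Sections 7, 12, 33 | Sections 3, 7 (no figure in the Table 1 arm labels) |
| Compliance row in Table 1 | Yes | None |
| Compliance tracking in the text | Section 33, monthly | None |
| Tolerability monitoring | Section 18 | Section 18 |
| Listed record of what was given | Issue and compliance rows | None |
| Delivery summary in Section 7 or 13 | None | None |

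The fifth row is the gap. For the drug, an adherence result could be built from what is collected. For the dialysate there is nothing listed to build it from.

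**Step 2. Whether another provision fills the gap.**

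- Section 13 analyzes patients by assignment, whether or not the treatment was given as planned. That is the right main analysis. It allows for departures but does not measure them.
- Section 14 has the independent monitor check source documents against the data collected. An item that is not collected is not part of that comparison.
- Section 15 ends treatment for patients who cannot comply, but names no record that would show non-compliance with the temperature.

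**Step 3. Size.** Inputs: 24 intervention weeks (Table 1 title); 20 patients (Sections 3 and 13) or 25 (Section 7); 3 sessions a week (my assumption).

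- Sessions per patient: 24 × 3 = 72.
- Sessions in the trial: 72 × 20 = 1,440, or 72 × 25 = 1,800.
- At the table's own monthly marking, taking one flow sheet a month (also an assumption): 6 abstractions per patient during the intervention, so 6 × 20 = 120 or 6 × 25 = 150. These would cover 6 of 72 sessions, or 1 in 12.

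On either count, the number with a listed temperature is zero.

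**The case against.** The strongest reply is that a schedule of assessments is not a case report form. Section 16 leaves the collection forms to the investigators, and the flow sheet already in use may show the temperature. This stands as a limit: the conclusion is about the data as listed. A reader might infer that delivery can never be established. The documents do not support that, because they do not say what the flow sheet records.

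Second, *dialysate bath* is undefined and could be read to include temperature. It does not say so, and dialysate flow has its own entry. The table is also poorly laid out in the available copy, with an empty bullet after this list, so an argument from absence carries some uncertainty. Even on the generous reading there is no adherence row and no planned summary.

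Third, Section 3 says feasibility will be judged "by examining recruitment, retention, and key outcomes", and delivered temperature is not named. A reader might infer that half of the feasibility aim is lost. The documents attach no such fraction. What remains is that Section 1 names cool dialysate and Section 3 asks about maintenance on protocol.

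Fourth, a reader might infer from "maintain dialysate temperature according to physician's discretion, usually at 37 °C" that sessions will drift off assignment in both groups. That phrase describes US practice outside the trial. Section 18's expectation of feeling cold or shivering makes departures from the cool setting plausible, but nothing predicts control sessions run cool. The documents give no departure rate, so I offer no estimate of a diluted contrast.

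Finally, a null result for residual renal function in about 20 patients would be inconclusive even with perfect temperature records. That is fair. The loss is to the feasibility result and to planning, more than to a test of efficacy.

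**Conclusion.** The point holds for the data as listed. Temperature is a randomized factor. Table 1 names no temperature item, every compliance check concerns the study drug, and no other section supplies a delivery record. Followed as written, the pilot ends with adherence data for the pill and none for the dialysate.

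The size is 72 sessions per patient (1,440 to 1,800 in all) with no listed temperature, assuming 3 sessions a week for 24 weeks. The conclusion rests on the item list being complete and on *dialysate bath* not including temperature. If the sponsor confirms that the flow sheet or the collection form already captures temperature, the remaining gap is that the protocol does not require it to be abstracted, checked or reported.

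This should be corrected, but it does not invalidate the design or the intention-to-treat analysis. The two labels for the control temperature are a minor wording matter. They do not by themselves show that the control was set differently from 37 °C.

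**What to change.** 1. Confirm whether the chairside flow sheet records dialysate temperature. If it does not, identify another DCI record that does.
2. In Table 1, add *dialysate temperature (set)* to the HD treatment data, for all four arms. Abstract it for each intervention session if possible, and at minimum at each existing monthly abstraction.
3. Add a dialysate adherence row beside the drug compliance check.
4. In Section 7, add as a feasibility outcome, by arm, the percentage of abstracted sessions run at the assigned temperature and the mean set temperature.
5. Reconcile the control label between Section 3 and Table 1, so that adherence in the control arms has one definition.

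The cost is abstraction time: about 72 values per patient if per session (3 sessions a week for 24 weeks), or about 6 if monthly. For 20 patients that is 1,440 or 120 values. The per-session option also means moving beyond the monthly marking in Table 1. The monthly option is cheaper but, at one sheet a month, sees only 1 session in 12. Provided an existing record holds the temperature, neither option adds a procedure for patients.

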## 15. Withdrawal of Subjects

Subjects may withdraw from this study at any time. Subjects should notify the study PI or staff member of their intent to withdraw in writing. Information collected prior to withdrawal will remain part of the study.

Active treatment with the study interventions will be terminated if the patient:

- Withdraws their informed consent
- Is unable to follow/comply with study procedures
- Undergoes kidney transplantation
- Transfers to home dialysis
- Transfers care to a dialysis facility outside of the Albuquerque DCI clinics or Rio Rancho.
- Becomes pregnant while on study drug.

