# DIDIT: Diuretic/Cool Dialysate Trial

## 18. Risks to Subjects

**Hemodialysis:** may be associated with complications. Hemodialysis can lead to low blood pressure (25% of all dialysis sessions) which may result in abdominal discomfort, nausea, vomiting, muscle cramps, dizziness and anxiety. In addition, hemodialysis can lead to bleeding, tachycardia and other abnormal heart rhythms, electrolyte imbalances, clotting or infection of the vascular access, and rarely, death. ***However, the risks associated with HD would be present whether or not the patient chooses to participate in this study.*** It is unknown whether use of diuretic and cool dialysate will increase or decrease the risk of these complications.

**Cool dialysate (35.5°):** The most common complication for patients dialyzed with cool dialysate is feeling colder, and if severe, they may develop shivering.

Patients will be monitored for patient comfort during dialysis to assess cold intolerance that may occur with cool dialysate. If these symptoms are observed, then the PI will determine whether this is a safety endpoint.

**Bumetanide:** Muscle cramps, severe dizziness, and hearing changes, like ringing in the ears, are the most common side effects of bumetanide (1.1%). A very serious allergic reaction to this drug is also rare.

Patients will be monitored for hypersensitivity reaction or musculoskeletal symptoms to determine tolerability of patients to the diuretic.

**Psychological:** Participants may be asked some questions of a personal nature. They are free to decline to answer any question at any time.

**Loss of Privacy:** Participation in research may involve a loss of privacy. Steps will be taken to mitigate the risk related to confidentiality of study data.

**Pregnancy:** The risk(s) of cool dialysate and/or Bumetanide on a developing fetus are unknown; therefore, subjects who are pregnant or actively planning to become pregnant in the next 8 months will not be allowed to participate in this study.

Subjects of child-bearing potential will have a pregnancy blood test done prior to study randomization. Subjects that refuse pregnancy testing will not be allowed to participate in this study.

**Nursing Mothers:** It is not known whether Bumetanide is excreted in human milk. Breast feeding should not be undertaken while the participant is on this drug. Breast feeding females will not be allowed to participate in this study.

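### The only scheduled adverse-event list omits the harms the protocol names for bumetanide and cool dialysate and mixes in disposition items, and dizziness and hearing changes have no stated ascertainment

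*Combined protocol and SAP*

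**What the plan says.** - **Aim (Section 1):** "We aim to conduct a pilot randomized controlled trial (RCT) to assess feasibility and safety". Section 7 lists preliminary data on AEs and SAEs among the endpoints, along with retention and health care utilization.
- **Scheduled collection (Section 12, Table 1):** the Adverse Events row lists emergency room visits, hospitalizations, outpatient visits, mortality, transplantation, PD, "Transfer to other unit", relocation, "Hypotensive episode" and dialysis access events.
- **Named harms (Section 18):** "Muscle cramps, severe dizziness, and hearing changes, like ringing in the ears, are the most common side effects of bumetanide", with a rate of 1.1% and no denominator. Serious allergic reaction is called rare. For cool dialysate the section names feeling colder and, if severe, shivering.
- **Monitoring (Section 18):** "Patients will be monitored for hypersensitivity reaction or musculoskeletal symptoms to determine tolerability of patients to the diuretic". Comfort during dialysis is to be watched for cold intolerance, and the PI then decides whether such symptoms are a safety endpoint.
- **Causality (Section 14):** investigators relate each AE or SAE to hemodialysis frequency, the diuretic and/or iohexol.
- **Blinding (Section 3):** the protocol states that the intervention cannot be double-blinded. The diuretic is compared with placebo, and assessment of patient-reported outcomes is to be blinded.
- **Analysis (Section 13):** outcomes are summarized by arm. No AE test or pooled AE rate is specified.

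**The concern.** A pilot with a safety aim should collect, on a schedule, the harms it expects from its own interventions. Here the scheduled list and the expected harms do not overlap, and the text that partly bridges them gives no time, form or grading.

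Two things are at stake. The first is completeness: a symptom nobody is told to ask about is recorded only if the patient raises it and someone writes it down. The second is comparability. Section 18 ties each monitoring sentence to one intervention and does not ask for the same questions in all four arms. Staff who know the dialysate temperature may ask about cold more often where they expect it. Whether a cold symptom counts is then settled after it has occurred, by a PI who is not stated to be blinded. Tolerability figures gathered this way would be a weak basis for designing the full-scale trial.

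**Working it through.** The documents give no safety sample size, expected event count or AE rate by arm, so there is no planned figure to reproduce. The only precision statement, ±0.18 in Section 13, concerns retention and has no bearing here. The check is mainly textual.

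**Step 1. Named harms against stated ascertainment**

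| Harm named in Section 18 | In Table 1 AE row? | Monitoring stated in Section 18? |
|---|---|---|
| Muscle cramps (bumetanide) | No | Yes, as musculoskeletal symptoms |
| Severe dizziness (bumetanide) | No | No |
| Hearing changes (bumetanide) | No | No |
| Allergic reaction (bumetanide) | No | Yes, as hypersensitivity |
| Feeling cold, shivering (cool dialysate) | No | Yes, as cold intolerance; endpoint status left to the PI |

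None of the five is in the scheduled row. Three have monitoring without a recording schedule. Two have neither, and both are among the three side effects called most common.

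**Step 2. What the row contains.** Of ten top-level entries, five are disposition or utilization: outpatient visits, transplantation, PD, transfer and relocation. Section 15 treats comparable events as reasons to end study treatment, for example "Transfers care to a dialysis facility outside of the Albuquerque DCI clinics or Rio Rancho". The only sign or symptom in the row is the hypotensive episode, which Section 18 lists as a risk of hemodialysis itself.

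**Step 3. Causality.** The randomized factors are bumetanide versus placebo and 35.5 °C versus 37 °C. Section 14 names one of them (the diuretic), omits dialysate temperature, and adds hemodialysis frequency and iohexol, which are not study interventions.

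**Step 4. Scale.** Assume that 1.1% is a cumulative per-patient rate and that equal allocation of 20 patients puts 10 on bumetanide. The documents state neither.

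- P(at least one event) = 1 − (1 − p)^n. For p = 0.011 and n = 10: 1 − 0.989^10 = 0.105.
- At assumed true rates of 5%, 10% and 20%, with n = 10: 0.40, 0.65 and 0.89.
- Section 7 speaks of 25 patients. With 12 on bumetanide and p = 0.011: 0.124.
- If no event is seen in n patients, the one-sided 95% upper bound is 1 − 0.05^(1/n): 25.9% for n = 10 and 22.1% for n = 12.

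The zero-event bound assumes that every event would have been recorded. If the symptom was not asked about, it has no clear meaning.

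**Step 5. Background.** Section 18 also lists cramps and dizziness as possible results of low blood pressure during dialysis, which it puts at 25% of sessions. Reports of these two symptoms will therefore include events unrelated to the drug, and can be read only against the same question asked in the placebo arms.

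**The case against.** The strongest reply is that the Table 1 row need not define what counts as an adverse event. Section 14 requires causality assessment of AEs and SAEs generally, and an independent monitor reviews all captured data about every 3 months. The row may be a chart-abstraction checklist, and its disposition and utilization items serve the retention and utilization endpoints of Section 7. Section 18 does monitor cold intolerance, hypersensitivity and musculoskeletal symptoms, and Table 1 schedules a Dialysis Symptom Index at baseline and two later points.

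Most of this stands, and it rules out some stronger readings:

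- A reader might infer that the named harms would go largely unrecorded. The documents do not support that: three of the five have stated monitoring, and the symptom index may cover others. Its items are not given, so it can be neither credited nor dismissed.
- A reader might infer that disposition events would dominate the total AE rate. No such rate is planned, and no event frequencies are given.
- A reader might infer that a planned safety comparison would fail. None is planned, and with some 10 patients per factor level, better capture would not make one feasible.

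The placebo also limits arm-dependent reporting for the diuretic, so that risk is clearest for dialysate temperature.

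The reply does not close the gap. A general duty to assess events does not say how symptoms are elicited. The monitor sees only what has been captured. No step carries questionnaire answers into the AE record.

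**Conclusion.** The point holds as a gap in ascertainment and internal alignment. The only scheduled adverse-event collection lists none of the five harms named for the two interventions. Dizziness and hearing changes have no stated ascertainment, unless the symptom index happens to cover them. The other three have monitoring with no schedule or link to the AE row, and the status of cold symptoms is decided after the event. The causality sentence leaves out one of the two randomized factors.

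The consequence is a risk of incomplete or arm-dependent symptom data for a stated aim; the documents do not show that it would occur. The figures of about 10% for any event and 26% for the zero-event bound depend on the per-patient reading of 1.1% and on 10 patients taking bumetanide. They say nothing about cool dialysate, for which no rate is given. The change is worth making because it is cheap. The efficacy analyses are not affected.

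**What to change.** 1. Add five yes/no items to the Table 1 AE row: muscle cramps; dizziness; hearing change or tinnitus; hypersensitivity; cold intolerance or shivering. Ask them in the same words in all four arms and summarize them by arm.
2. Ask them at the coordinator's monthly drug-compliance contact described in Section 33. Table 1 marks only two compliance checks, so the two sections should first be made to agree.
3. Record every reported cold symptom, so that its inclusion does not depend on a later decision by the PI.
4. Keep transfer, relocation, transplantation, PD and outpatient visits for the retention and utilization endpoints, but label them separately from adverse events.
5. Reconcile Sections 12, 14 and 18: extend the Section 18 monitoring sentence to the side effects it names, say where those symptoms are recorded, and make the causality sentence refer to the two randomized factors.

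The cost is a form edit, a few more questions per contact and more reported non-serious events. If the AE row is now filled from charts only, asking patients directly is a small new procedure. With about 20 patients the results remain descriptive and do not support a safety comparison.
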